8.1 Rezafungin for Injection

8.1.1 Formulation

Rezafungin for Injection is a lyophilized formulation of the active pharmaceutical ingredient, rezafungin acetate. Rezafungin for Injection is supplied in vials as a sterile lyophilized powder (200 mg) for reconstitution prior to dilution into normal saline infusion bags (250 mL). Excipients for rezafungin include polysorbate 80, histidine, and mannitol.

8.1.2 Directions for Use

Rezafungin for Injection is administered IV with a 400 mg loading dose on Day 1 of Week 1, followed by 200 mg once weekly, for a total of 2 to 4 doses.

Intravenous infusion of Rezafungin for Injection and IV placebo is administered over 60 (± 10) minutes, although the infusion time may be increased up to 180 minutes as needed to manage evolving symptoms of infusion reaction consistent with management of echinocandin class infusion reactions, whereby decreasing the rate of infusion often alleviates symptoms. Dosage adjustments of Rezafungin for Injection are not allowed. Treatment will be initiated on an inpatient basis; a switch to outpatient IV treatment is allowed at the Investigator's discretion.

8.1.3 Drug Storage

Vials of Rezafungin for Injection and infusion bags with diluted Rezafungin for Injection should be stored per the directions presented in the study Pharmacy Manual.

8.1.4 Dose Adjustment

Dosage adjustments are not allowed in this study.

8.2 Placebo and Comparator Treatment

8.2.1 Placebo

In this double-blind, double-dummy, active comparator study, two placebo regimens are required; one for subjects randomized to Rezafungin for Injection and one for subjects randomized to caspofungin. In addition, because subjects in the caspofungin arm may be switched to oral step-down therapy, an oral placebo is required for subjects in the Rezafungin for Injection arm. Thus, placebo requirements for each treatment assignment are as follows:

Treatment Assignment	Placebo
Rezafungin for Injection	Placebo for caspofungin IV Placebo for oral step-down therapy (fluconazole)
Caspofungin IV	Placebo for Rezafungin for Injection

In more detail, placebo regimens for each treatment assignment are as follows:

Placebo Regimen for Rezafungin for Injection Treatment Assignment

Subjects will receive a caspofungin IV equivalent regimen of daily placebo IV infusion in a blinded manner. Because subjects randomized to caspofungin may be switched to fluconazole oral step-down therapy, a fluconazole-equivalent regimen of daily oral placebo will be administered for subjects randomized to Rezafungin for Injection at that time.

Placebo Regimen for Caspofungin IV Treatment Assignment

Subjects who are switched to fluconazole oral step-down therapy will receive a Rezafungin for Injection equivalent regimen of weekly placebo IV infusion in a blinded manner.

8.2.2 Caspofungin

Anaphylaxis has been reported with administration of caspofungin. If this occurs, caspofungin should be discontinued immediately and appropriate treatment administered.

Possible histamine-like reactions, including rash, facial swelling, sensation of warmth, pruritis, and bronchospasm, have been observed during infusion of caspofungin. These reactions may require discontinuation of the infusion and/or administration of appropriate treatment.

Cases of Stevens-Johnson Syndrome and toxic epidermal necrolysis have been reported after post-marketing use of caspofungin.

Finally, abnormal liver function tests have been observed with healthy volunteers and patients treated with caspofungin. In patients with serious underlying conditions, cases of clinically significant hepatic dysfunction, hepatitis, and hepatic failure have been reported without a causal relationship established.

Levels of caspofungin may increase with concomitant administration of cyclosporine and may decrease with concomitant use of efavirenz, nevirapine, rifampin, dexamethasone, phenytoin, and carbamazepine.

See [Appendix 7A](#) for potential caspofungin drug interactions, warnings, and precautions. The list is not exhaustive, and the Investigator must refer to the US Prescribing Information or Summary of Product Characteristics (SmPC).

8.2.2.1 Formulation

Caspofungin IV is provided in its commercial formulation. Excipients for caspofungin include sucrose, mannitol, glacial acetic acid, and sodium hydroxide (refer to the US Prescribing Information or SmPC for excipients used in specific generic versions).

8.2.2.2 Directions for Use

The manufacturer's instructions for caspofungin dose preparation should be followed.

Subjects randomized to caspofungin will receive a total treatment of ≥ 14 days beginning with a single caspofungin 70 mg IV loading dose on Day 1 followed by 50 mg once daily with the option to continue treatment ≤ 28 days, unless they qualify for an alternative caspofungin regimen per [Section 8.2.2.4](#) or for step-down therapy after ≥ 3 days (or the minimum duration of IV therapy advised by the site's national/regional/local guidelines, whichever is greater) of caspofungin IV treatment per [Section 8.2.3](#). Doses are to be administered 24 (± 2) hours after the start of study drug administration on the previous day. The infusion time for caspofungin is the same as for Rezafungin for Injection. The infusion time of time of 60 (± 10) minutes may be increased as needed up to 180 minutes to manage evolving symptoms of infusion reaction consistent with management of echinocandin class infusion reactions, whereby decreasing the rate of infusion often alleviates symptoms.

8.2.2.3 Drug Storage

The manufacturer's instructions for caspofungin storage should be followed.

8.2.2.4 Dose Adjustment

Subjects with moderate hepatic impairment (Child-Pugh score of 7–9): loading dose of caspofungin of 70 mg on Day 1 followed by 35 mg once daily.

Subjects weighing >80 kg or on concomitant rifampin, nevirapine, efavirenz, phenytoin, dexamethasone, or carbamazepine: caspofungin 70 mg once daily. Dose adjustment due to DDIs or weight may be considered according to the approved labeling and at the Investigator's discretion.

Use of concomitant cyclosporine should be limited to subjects for whom potential benefit outweighs potential risk of DDIs and hepatotoxicity with caspofungin.

8.2.3 Oral Step-Down Therapy: Fluconazole

Fluconazole should not be co-administered with terfenadine, cisapride, astemizole, erythromycin, pimozide, quinidine, halofantrine, or any other drug metabolized via the CYP3A4 enzymatic pathway and may cause prolongation of the QT interval.

Fluconazole is a potent CYP2C9 inhibitor and a moderate CYP3A4 inhibitor and thus all subjects on fluconazole who are concomitantly taking drugs that are also metabolized through these pathways should be monitored closely.

See [Appendix 7B](#) for potential fluconazole drug interactions, warnings, and precautions. The list is not exhaustive, and the investigator must refer to the US Prescribing Information or SmPC.

8.2.3.1 Formulation

Commercial fluconazole tablets have been over-encapsulated for study blinding. Excipients for fluconazole include microcrystalline cellulose, dibasic calcium phosphate anhydrous, povidone, croscarmellose sodium, FD&C Red Dye No. 40 aluminum lake dye, and magnesium stearate.

8.2.3.2 Directions for Use

After ≥ 3 days of caspofungin treatment (or the minimum duration of IV therapy advised by the site's national/regional/local guidelines, whichever is greater), subjects who meet the step-down therapy eligibility criteria may be switched to oral fluconazole (earliest oral dose on Day 4 or later, as advised by a site's national/regional/local guidelines). The total comparator treatment period (caspofungin plus fluconazole) is ≤ 28 days. Subjects with a creatinine clearance > 50 mL/min (see [Appendix 2](#)) will receive oral fluconazole at a dose of 6 mg/kg administered once daily rounded to the nearest 200 mg increment with a maximum daily dose of 800 mg (e.g., a subject weighing 73 kg would receive a fluconazole 400 mg dose [2 capsules of 200 mg each] based on a 6 mg/kg target dose [$73 \text{ kg} \times 6 \text{ mg/kg} = 438 \text{ mg}$]). Subjects with creatinine clearance ≤ 50 mL/min will receive oral fluconazole at a dose of 3 mg/kg administered once daily rounded to the nearest 200 mg increment with a maximum daily dose of 400 mg (e.g., a subject

weighing 73 kg would receive a fluconazole 200 mg dose [1 capsule of 200 mg] based on a 3 mg/kg target dose [73 kg × 3 mg/kg = 219 mg]. Subjects receiving hemodialysis receive the same dose as subjects with a creatinine clearance >50 mL/min; however, they are only dosed following hemodialysis. Subjects receiving continuous renal replacement therapy (CRRT) should be treated as a subject with normal renal function at 6 mg/kg rounded to the nearest 200 mg each day (Cousin 2003). Subjects receiving peritoneal dialysis should be treated with 1.5 mg/kg rounded to the nearest 200 mg each day (Cousin 2003).

Investigators are advised to pay close attention to signs of overdosing and underdosing with underweight (<50 kg) and overweight (>85 kg) subjects, respectively. Additionally, signs of potential fluconazole toxicity, including hepatic toxicity and QT prolongation, should be closely monitored for any subject on oral step-down therapy. Subjects weighing over 130 kg will not be eligible for oral step-down therapy.

8.2.3.3 Oral Step-Down Therapy Eligibility Criteria

An oral step-down therapy is allowed in both treatment groups (fluconazole for caspofungin, placebo for oral step-down therapy for Rezafungin for Injection), provided the following criteria are met:

- Able to take oral medication
- ≥ 3 days of IV study drug (or the minimum duration of IV therapy advised by the site's national/regional/local guidelines, whichever is greater)
- The *Candida* spp. isolated is susceptible to fluconazole
- All signs and symptoms of candidemia and/or invasive candidiasis that were present at baseline have resolved
- The subject's clinical status is considered stable based on Investigator assessment
- Most recent blood culture must be drawn following the first dose of study drug AND ≥ 48 hours prior to oral study drug initiation AND must be negative for *Candida* spp.
- No evidence of moderate or severe hepatic injury (alanine aminotransferase or aspartate aminotransferase $>5\times$ the ULN)
- No history of hypersensitivity to any azole or any other contraindications to the use of fluconazole or its excipients (Appendix 7B), including concomitant use of the following medications: terfenadine, cisapride, astemizole, erythromycin, pimozide, and quinidine
- No personal or family history of Long QT interval on ECG (QT) syndrome or a prolonged QT interval corrected for heart rate by Fridericia's formula (QTcF) interval (>470 msec in males and >480 msec in females)
- In the Investigator's opinion, the subject can tolerate oral fluconazole therapy (refer to current fluconazole Prescribing Information)

- Subject's weight is ≤ 130 kg

While QT prolongation is rare with fluconazole without the contraindicated interacting medications listed above, investigators should monitor subjects with ECGs as clinically indicated.

Subjects who are switched to oral step-down therapy may switch back to IV study drug therapy in the event of the development of an unforeseen condition that prevents the subject from taking oral medications (e.g., pancreatitis, urgent surgery), but may not switch back to IV study drug therapy for worsening or relapse of candidemia/invasive candidiasis or for intolerance or toxicity due to study drug.

The daily dosing schedule with options for the required treatment period is presented in [Figure 2](#) and for the optional treatment period is in [Figure 3](#). The daily dosing schedule for the entire study period (required and optional) is presented in [Table 3](#).

8.2.3.4 Drug Storage

Capsule containing fluconazole tablets (over-encapsulated fluconazole) should be stored per the directions presented in the study Pharmacy Manual.

8.2.3.5 Dose Adjustment for Renal Impairment

Subjects with creatinine clearance ≤ 50 mL/min (see [Appendix 2](#)) will receive oral fluconazole at a dose of 3 mg/kg administered once daily rounded to the nearest 200 mg increment with a maximum daily dose of 400 mg. Subjects receiving hemodialysis receive the same dose as subjects with a creatinine clearance >50 mL/min; however, they are only dosed following hemodialysis. Subjects receiving CRRT should be treated as a subject with normal renal function at 6 mg/kg rounded to the nearest 200 mg each day ([Cousin 2003](#)). Subjects receiving peritoneal dialysis should be treated with 1.5 mg/kg rounded to the nearest 200 mg each day ([Cousin 2003](#)).

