- ^h Blood will be collected pre-dose (≤30 minutes prior to the start of the infusion).
- ⁱ Presence of central line during Screening or placed during the study should be documented with dates of insertion and removal. Short-term central venous catheters (e.g., peripherally-inserted central catheters, internal jugular, or subclavian central venous catheters) and long-term central venous catheters (e.g., tunneled catheters) are recommended to be removed within 48 hours after diagnosis with candidemia, consistent with IDSA and ESCMID guidelines.

Table 3: Dosing Schedule by Day

Study Day Regimen ^a	Randomized Treatment	
	Rezafungin for Injection	Caspofungin ^b with Oral Step-Down Option
1	Rezafungin for Injection 400 mg IV	caspofungin 70 mg IV (loading dose)
2–3	placebo for caspofungin IV	caspofungin 50 mg IV
>3	Optional switch to oral step-down therapy allowed ^c	
4–7		
IV only	placebo for caspofungin IV	caspofungin 50 mg IV
oral step-down	placebo for oral step-down therapy	oral step-down therapy (fluconazole)
8 (±1)		
IV only	Rezafungin for Injection 200 mg IV	caspofungin 50 mg IV
oral step-down	Rezafungin for Injection 200 mg IV -and- placebo for oral step-down therapy	placebo for Rezafungin for Injection IV -and- oral step-down therapy (fluconazole)
9–14		
IV only	placebo for caspofungin IV	caspofungin 50 mg IV
oral step-down	placebo for oral step-down therapy	oral step-down therapy (fluconazole)
15–28	Optional treatment period begins. An End of Treatment visit is required within 2 calendar days after the last dose of study drug.	
15 (±1)		
IV only	Rezafungin for Injection 200 mg IV	caspofungin 50 mg IV
oral step-down	Rezafungin for Injection 200 mg IV -and- placebo for oral step-down therapy	placebo for Rezafungin for Injection IV -and- oral step-down therapy (fluconazole)
16–21		
IV only	placebo for caspofungin IV	caspofungin 50 mg IV
oral step-down	placebo for oral step-down therapy	oral step-down therapy (fluconazole)
22 (±1)		
IV only	Rezafungin for Injection 200 mg IV	caspofungin 50 mg IV
oral step-down	Rezafungin for Injection 200 mg IV -and- placebo for oral step-down therapy	placebo for Rezafungin for Injection IV -and- oral step-down therapy (fluconazole)
23–28		
IV only	placebo for caspofungin IV	caspofungin 50 mg IV
oral step-down	placebo for oral step-down therapy	oral step-down therapy (fluconazole)

Abbreviation: CRRT = continuous renal replacement therapy; IV = intravenous(ly).

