6.5 Method of Treatment Assignment and Blinding

After informed consent has been obtained, subjects will be screened for study eligibility before randomization.

Subjects will be randomly assigned (1:1 ratio) to receive either Rezafungin for Injection or caspofungin. Randomization will be stratified based on diagnosis (candidemia only; invasive candidiasis) and by Acute Physiology and Chronic Health Evaluation (APACHE II) score/ absolute neutrophil count (ANC) (APACHE II score ≥ 20 OR ANC < 500 cells/ μL ; APACHE II score < 20 AND ANC ≥ 500 cells/ μL) at Screening. If a subject has a positive result

for both blood culture/rapid IVD and culture specimen obtained from a normally sterile site, the subject will be randomized within the invasive candidiasis stratum.

The study site's pharmacist (or pharmacist designee) will obtain the study drug assignment via an Interactive Response Technology (IRT). Randomized subjects will be assigned the treatment corresponding to the next available randomization number from the computer-generated randomization schedule. A subject is considered randomized when a randomization transaction is recorded in the IRT.

All study personnel, including the Sponsor, Investigator, and site personnel involved in study conduct, and subjects will remain blinded to study medication assignment until the study is completed and the database is locked with the exception of the pharmacy monitor, unblinded project manager, clinical supplies, document manager, and quality (per the Sponsor Blinding Plan) who may be unblinded to study medication at any time during study conduct. The DSMB will be unblinded to safety data for periodic safety reviews as defined in the DSMB Charter. The Pharmacy Monitor will monitor study drug preparation and accountability during the study and cases in which unblinding is required due to a safety or tolerability issue. To maintain study blinding, study drug preparation will be performed by an unblinded site pharmacist (or qualified unblinded personnel at the study site not involved with study procedures or evaluations).

Instructions for study drug preparation and dosing are outlined in the Pharmacy Manual provided separately to the site. To maintain the blind, oral study drug pills must never be crushed. In the case of a medical emergency requiring the Investigator to know the identity of the study drug, the Investigator will follow the procedures outlined in [Section 8.4](#).

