An insufficient therapeutic effect may be determined prior to the planned duration of therapy in the study. This determination will require an assessment of clinical status including the synthesis of symptoms and signs data (both local and systemic). Subjects who are deemed to have an insufficient therapeutic effect should be discontinued from study drug therapy.

If a subject has daily blood cultures positive for *Candida* spp. through Day 7 despite appropriate study drug administration, this should be considered an insufficient therapeutic effect and study drug should be discontinued and salvage therapy initiated. The subject should remain in the study through the Follow-up visit (Days 52–59) to complete safety assessments and assess for mortality.

Seven days is the maximum number of daily positive blood cultures allowed prior to a change in antifungal therapy. The Investigator may determine that there is an insufficient therapeutic response prior to Day 7.

- Investigator discretion
 - Resistant Pathogen(s): In the event an organism resistant to ≥ 1 of the potential study drugs is isolated, the Investigator will determine whether the subject remains on study drug therapy. The Investigator may decide to continue study drug therapy if, in the Investigator's opinion, there is clear and continuing clinical improvement while on therapy.
 - The Investigator may decide to prematurely discontinue study drug therapy and to initiate an alternative and appropriate therapy if, in the Investigator's opinion, the subject is not benefiting from study drug.

NOTE: The Medical Monitor should be contacted to discuss whether to continue or prematurely discontinue a subject on the study drug in the event the subject requires systemic concomitant antifungal therapy.

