In the event salvage therapy is required due to either insufficient therapeutic effect or Investigator discretion, the Investigator should note that since the subject has failed echinocandin therapy, other echinocandins may not be the best choice for salvage therapy. If the subject is switched to oral step-down therapy prior to study drug failure, the Investigator should consider that subjects in the caspofungin arm will also have been taking fluconazole. In both circumstances, the Investigator should refer to the IDSA ([Pappas 2016](#)) or ESCMID ([Cornely 2012](#); [Ullmann 2012](#)) guidelines for treatment failure in candidemia, and will need to determine whether or not breaking the blind is necessary to make an informed choice of future antifungal therapies.

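### The peritoneal-dialysis fluconazole rule gives 0 mg below 66.7 kg, and no minimum dose is stated

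*Protocol*

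**What the plan says.** Protocol 8.2.3.5 gives the peritoneal-dialysis dose: "Subjects receiving peritoneal dialysis should be treated with 1.5 mg/kg rounded to the nearest 200 mg each day". The same sentence appears in the Synopsis (fluconazole step-down regimen), the Table 3 footnote, Section 8.2.3.2 and the SAP Appendix 4 footnote.

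Section 8.2.3.2 shows how rounding is meant to work. A 73 kg subject at 6 mg/kg (438 mg) receives 400 mg as two capsules, and at reduced renal function a subject "weighing 73 kg would receive a fluconazole 200 mg dose [1 capsule of 200 mg] based on a 3 mg/kg target dose" (219 mg). The only capsule strength described is 200 mg. For creatinine clearance of 50 mL/min or less, subjects "will receive oral fluconazole at a dose of 3 mg/kg administered once daily rounded to the nearest 200 mg increment".

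The limits that are stated all lie at the upper end: daily maxima of 800 mg and 400 mg for the 6 and 3 mg/kg rules, and a step-down weight ceiling of 130 kg (8.2.3.3). For light subjects there is only monitoring advice, to watch for "signs of overdosing and underdosing with underweight (<50 kg) and overweight (>85 kg) subjects, respectively".

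**The concern.** A rule that scales with weight and then rounds to a coarse unit needs a floor, or it returns zero at the low end. At 1.5 mg/kg with a 200 mg unit, the low end falls within ordinary adult weights.

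A zero dose contradicts the sentence itself, which says these subjects are to be treated each day. It also sits badly with Table 3. After step-down, the caspofungin arm's daily IV drug is replaced by fluconazole, and the only infusions left are weekly placebo. A caspofungin-arm subject dosed literally would therefore have no active study antifungal, whereas a rezafungin-arm subject would lose only oral placebo. Under 8.2.3.3 a subject may not return to IV study drug because of worsening or relapse.

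The realistic risk is less dramatic. Each site has to improvise, and sites may improvise differently from the same sentence in a double-blind trial.

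**Working it through.** **Inputs.** Dose rate k: 6, 3 or 1.5 mg/kg (8.2.3.2 and 8.2.3.5). Rounding unit: 200 mg. Upper weight for step-down: 130 kg (8.2.3.3). Lower weight: none stated.

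**Formula.** Dose = 200 × floor(k × w / 200 + 0.5), with w in kg.

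**The protocol's own examples (73 kg).**
- 6 × 73 = 438; 438/200 = 2.19, rounds to 2, giving 400 mg. Matches.
- 3 × 73 = 219; 219/200 = 1.095, rounds to 1, giving 200 mg. Matches.

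**Where each rule reaches zero.** The result is 0 when k × w < 100, that is w < 100/k:
- 6 mg/kg: below 16.7 kg
- 3 mg/kg: below 33.3 kg
- 1.5 mg/kg: below 66.67 kg

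At ordinary adult weights only the peritoneal-dialysis rule is affected. Its next step, to 400 mg, would need 300/1.5 = 200 kg, above the 130 kg ceiling. Over the eligible range it can therefore return only 0 or 200 mg.

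| Weight (kg) | 1.5 mg/kg target (mg) | Rounded (mg) | 3 mg/kg target (mg) | Rounded (mg) | One capsule ÷ 1.5 mg/kg target |
|---|---|---|---|---|---|
| 45 | 67.5 | 0 | 135 | 200 | 2.96 |
| 50 | 75 | 0 | 150 | 200 | 2.67 |
| 55 | 82.5 | 0 | 165 | 200 | 2.42 |
| 60 | 90 | 0 | 180 | 200 | 2.22 |
| 66 | 99 | 0 | 198 | 200 | 2.02 |
| 66.7 | 100.05 | 200 | 200.1 | 200 | 2.00 |
| 73 | 109.5 | 200 | 219 | 200 | 1.83 |
| 130 | 195 | 200 | 390 | 400 | 1.03 |

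The last column is 200/(1.5 × w); for example, 200/90 = 2.22 at 60 kg. The rule already accepts twice the target at 66.7 kg, then drops to nothing just below that weight.

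**Search for a rescue.** None of the five copies carries a minimum dose or a round-up instruction. Peritoneal dialysis is not an exclusion criterion in Section 7.2, and the existence of a dedicated sentence shows that these subjects were foreseen.

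**The case against.** The best reply is that nobody would follow the rule to zero. The sentence calls for treatment each day, the smallest dose in the worked examples is one capsule, and the rule gives exactly one capsule at every eligible weight from 66.7 kg. Staff may also keep the subject on IV study drug, because step-down is optional. Section 6.5 adds that "Instructions for study drug preparation and dosing are outlined in the Pharmacy Manual provided separately to the site", and that manual, not among the documents reviewed, may already set a floor.

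The numbers affected must also be small. Active drug is at issue only for a caspofungin-arm subject on peritoneal dialysis, under 66.7 kg, with resolved signs and symptoms, stable status, a negative blood culture and a fluconazole-susceptible isolate. Section 7.4.2 provides for changing treatment if the subject then worsens: "In the event salvage therapy is required due to either insufficient therapeutic effect or Investigator discretion", the investigator is directed to treatment guidelines.

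Timing limits the benefit further. SAP 1.2.2 puts the last primary-enrollment randomization on 16 August 2021. With dosing ending by Day 28, that cohort finished around mid-September, before SAP V4.0 of 2 November 2021. Only the China extension could still gain.

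Two smaller points are fair. Table 3 is not an absolute daily requirement, since its footnote has hemodialysis subjects dosed only after dialysis. And the caution for subjects under 50 kg concerns overdosing, which weighs against giving them a full capsule.

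All of this limits the consequences, and the last point bears on the choice of remedy. None of it makes the sentence correct: having to infer the intended dose from a rule that computes to zero is the defect.

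**Conclusion.** The concern holds. As written, the peritoneal-dialysis rule gives 0 mg at any weight below 66.67 kg, and nothing in either document corrects it. From 66.7 to 130 kg it gives one capsule and can be followed.

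The impact is low to moderate. It is a dosing-rule error that should be fixed, but it does not touch an endpoint, an analysis or the power calculation. The arithmetic rests on the rounding convention in the protocol's own examples. The view that few subjects are affected is a judgement, because the documents give no count of peritoneal-dialysis subjects. Whether sites hold a correcting instruction cannot be settled without the Pharmacy Manual.

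**What to change.** In the Synopsis, the Table 3 footnote, Sections 8.2.3.2 and 8.2.3.5, and the SAP Appendix 4 footnote, add a minimum of one 200 mg capsule daily for peritoneal dialysis. Because 1.5 × 130 = 195 mg also rounds to 200 mg, the sentence can be reduced to a flat 200 mg (one capsule) each day at every eligible weight.

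The downside is exposure of 2 to 3 times the 1.5 mg/kg target at 45 to 66 kg. That is the same 200 mg the 3 mg/kg rule gives at those weights, but the protocol sets peritoneal dialysis at half that rate, so the clinical team should confirm the dose. If they do not accept it, make peritoneal-dialysis subjects under 66.7 kg ineligible for oral step-down in both arms. They then stay on IV study drug and the blind is kept.

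Align the Pharmacy Manual. Notify the China sites if country-specific amendment A5-CN (cited in SAP 1.2.2, not provided) carries the same sentence. The cost is one sentence in four protocol places, one SAP footnote, a manual check and possibly a short letter. Sample size, endpoints and analyses do not change.
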